11.1.2 Serious adverse event (SAE)

A serious adverse event (SAE) is any adverse event, occurring at any dose and regardless of causality that:

- Results in death
- Is life-threatening. Life-threatening means that the person was at immediate risk of death from the reaction as it occurred, i.e., it does not include a reaction which hypothetically might have caused death had it occurred in a more severe form.

- Requires or prolongs inpatient hospitalization (i.e., the event required at least a 24-hour hospitalization or prolonged a hospitalization beyond the expected length of stay). Hospitalization admissions and/or surgical operations scheduled to occur during the study period, but planned prior to study entry, are not considered SAEs if the illness or disease existed before the person was enrolled in the trial, provided that it did not deteriorate in an unexpected manner during the trial (e.g., surgery performed earlier than planned). Surgery to remove the primary oral cavity lesion and/or nodal disease, or any additional surgery performed as a result of this surgery is also not considered an SAE.
- Results in persistent or significant disability/incapacity. Disability is defined as a substantial disruption of a person's ability to conduct normal life functions. This does not include expected side effects of planned surgery.
- Is a congenital anomaly or birth defect; or
- Is an important medical event when, based upon appropriate medical judgment, it may jeopardize the participant and require medical or surgical intervention to prevent one of the outcomes listed above. Examples of such medical events include allergic bronchospasm requiring intensive treatment in an emergency room or at home; blood dyscrasias or convulsions that do not result in inpatient hospitalization, or the development of drug dependency or drug abuse.

Events **not** considered to be serious adverse events are hospitalizations for:

- routine treatment or monitoring of the studied indication, not associated with any deterioration in condition, or for elective procedures
- elective or pre-planned treatment for a pre-existing condition that did not worsen
- emergency outpatient treatment for an event not fulfilling the serious criteria outlined above and not resulting in inpatient admission
- respite care

11.1.3 Expectedness

Adverse events can be 'Expected' or 'Unexpected.'

11.1.3.1 Expected adverse event

Expected adverse events are those that have been previously identified as resulting from administration of the agent. For the purposes of this study, an adverse event is considered expected when it appears in the current adverse event list, the Investigator's Brochure, the package insert or is included in the informed consent document as a potential risk.

11.1.3.2 Unexpected adverse event

For the purposes of this study, an adverse event is considered unexpected when it varies in nature, intensity or frequency from information provided in the current adverse event list, the Investigator's Brochure, or the package insert or when it is not included in the informed consent document as a potential risk.

11.1.4 Attribution

CONFIDENTIAL

This document is confidential. Do not disclose or use except as authorized.

Attribution is the relationship between an adverse event or serious adverse event and the study treatment. Attribution will be assigned as follows:

- Definite – The AE is clearly related to the study treatment.
- Probable – The AE is likely related to the study treatment.
- Possible – The AE may be related to the study treatment.
- Unlikely - The AE is doubtfully related to the study treatment.
- Unrelated - The AE is clearly NOT related to the study treatment.

11.2 Procedures for AE and SAE Recording and Reporting

Investigators will assess the occurrence of AEs and SAEs at all participant evaluation time points during the study.

All AEs and SAEs whether reported by the participant, discovered during questioning, directly observed, or detected by physical examination, laboratory test or other means, will be recorded in the participant's medical record and on the appropriate study-specific case report forms.

The descriptions and grading scales found in the CTEP Active Version of the NCI Common Terminology Criteria for Adverse Events (CTCAE version 4.0) will be utilized for AE reporting. The CTEP Active Version of the CTCAE version 4.0 is identified and located on the CTEP website at:

http://ctep.cancer.gov/protocolDevelopment/electronic_applications/ctc.htm.

All appropriate treatment areas should have access to a copy of the CTEP Active Version of CTCAE.

11.3 Reporting Requirements for Participating Investigators

Each participating investigator is required to abide by the reporting requirements set by the DF/HCC. The study must be conducted in compliance with FDA regulations, local safety reporting requirements, and reporting requirements of the principal investigator.

It is the responsibility of each participating investigator to report adverse events within 48 hours to the Overall PI, [name], MD, MPH (at the contact given below), or representative personnel; and submit to DFCI IRB within 10 working days.

[name], MPH
[contact]
[contact]

11.4 Reporting Requirements for DFCI IRB

CONFIDENTIAL

This document is confidential. Do not disclose or use except as authorized.

Investigators **must** report to the Overall PI any serious adverse event (SAE) that occurs after the initial dose of study treatment, during treatment, or within 30 days of the last dose of treatment (C2D1) on the local institutional SAE form.

Investigative sites within DF/HCC will report AEs directly to the DFCI Office for Human Research Studies (OHRS) per the DFCI IRB reporting policy.

Other investigative sites will report AEs to their respective IRB according to the local IRB’s policies and procedures in reporting adverse events. A copy of the submitted institutional AE form should be forwarded to the Overall PI within the timeframes detailed in the table below.

Attribution	DF/HCC Reportable AEs				
	Gr. 2 & 3 AE Expected	Gr. 2 & 3 AE Unexpected	Gr. 4 AE Expected	Gr. 4 AE Unexpected	Gr. 5 AE Expected or Unexpected
Unrelated Unlikely	Not required	Not required	5 calendar days [#]	5 calendar days	24 hours*
Possible Probable Definite	Not required	5 calendar days	5 calendar days [#]	5 calendar days	24 hours*
[#] If listed in protocol as expected and not requiring expedited reporting, event does not need to be reported.					
* For participants enrolled and actively participating in the study or for AEs occurring within 30 days of the last intervention, the AE should be reported within 1 business day of learning of the event.					

The overall PI will submit AE reports from outside institutions to the DFCI OHRS according to DFCI IRB policies and procedures in reporting adverse events.

11.5 Expedited Reporting to Hospital Risk Management

Participating investigators will report to DFCI Risk Management office any participant safety reports or sentinel events that require reporting according to institutional policy.

11.6 Reporting Requirements for FDA

There will be no submissions to the FDA as this protocol is deemed IND exempt.

11.7 Reporting Requirements for BMS

The Overall PI, or representative personnel; as soon as possible under the circumstances, will notify BMS of any serious adverse events (within 48 hours of learning about the event).

A report will be sent for any serious adverse event (SAE) that occurs after the initial dose of study treatment, during treatment, or within 30 days of the last dose of treatment (C2D1).

BMS contact for SAE reports:

Email: [contact]

[contact]

11.8 Monitoring of Adverse Events and Period of Observation

All adverse events, both serious and non-serious, and deaths that are encountered from initiation of study intervention through the study intervention period and up to 30 days after the last study intervention (C2D1) should be followed to their resolution, or until the participating investigator assesses them as stable, or the participating investigator determines the event to be irreversible, or the participant is lost to follow-up. The presence and resolution of AEs and SAEs (with dates) should be documented on the appropriate case report form and recorded in the participant's medical record to facilitate source data verification.

For some SAEs, the study sponsor or designee may follow-up by telephone, fax, and/or monitoring visit to obtain additional case details deemed necessary to appropriately evaluate the SAE report (e.g., hospital discharge summary, consultant report, or autopsy report).

Participants should be instructed to report any serious post-study event(s) that might reasonably be related to participation in this study. Participating investigators should notify the DF/HCC Overall Principal Investigator of any unanticipated death or adverse event occurring after a participant has discontinued or terminated study participation that may reasonably be related to the study.

12. DATA AND SAFETY MONITORING

12.1 Data Reporting

12.1.1 Method

The ODQ will collect, manage, and monitor data for this study.

Note: All adverse events that have occurred on the study, including those reported through AdeERS, must be reported via CTMS or CDUS.

12.1.2 Data Submission

The schedule for completion and submission of case report forms (paper or electronic) to the ODQ is as follows:

Form	Submission Timeline
Eligibility Checklist	Complete prior to enrollment with ODQ
On Study Form	Within 21 days of enrollment

CONFIDENTIAL

This document is confidential. Do not disclose or use except as authorized.

Baseline Assessment Form	Within 21 days of enrollment
Treatment Form	Within 14 days of the last day of the cycle
Adverse Event Report Form	Within 14 days of the last day of the cycle
Response Assessment Form	Within 14 days of the completion of the cycle required for response evaluation
Off Treatment/Off Study Form	Within 21 days of completing treatment or being taken off study for any reason
Follow up/Survival Form	Within 21 days of the protocol defined follow up visit date or call

12.2 Safety Meetings

The DF/HCC Data and Safety Monitoring Committee (DSMC) will review and monitor toxicity and accrual data from this trial. The committee is composed of clinical specialists with experience in oncology and who have no direct relationship with the study. Information that raises any questions about participant safety will be addressed with the Principal Investigator and study team.

The DSMC will meet quarterly and/or more often if required to review toxicity and accrual data. Information to be provided to the committee may include: up-to-date participant accrual; current dose level information; DLT information; all grade 2 or higher unexpected adverse events that have been reported; summary of all deaths occurring within 30 days for Phase I or II protocols; any response information; audit results, and a summary provided by the study team. Other information (e.g. scans, laboratory values) will be provided upon request.

12.3 Monitoring

Involvement in this study as a participating investigator implies acceptance of potential audits or inspections, including source data verification, by representatives designated by the DF/HCC Overall Principal Investigator or DF/HCC. The purpose of these audits or inspections is to examine study-related activities and documents to determine whether these activities were conducted and data were recorded, analyzed, and accurately reported in accordance with the protocol, institutional policy, Good Clinical Practice (GCP), and any applicable regulatory requirements.

All data will be monitored for timeliness of submission, completeness, and adherence to protocol requirements. Monitoring will begin at the time of participant enrollment and will continue during protocol performance and completion.

12.4 Multi-Center Guidelines

CONFIDENTIAL

This document is confidential. Do not disclose or use except as authorized.

This protocol will adhere to the policies and requirements of the DF/HCC Multi-Center Data and Safety Monitoring Plan. The specific responsibilities of the Overall PI, Coordinating Center, and Participating Institutions and the procedures for auditing are presented in Appendix D.

- *The Overall PI/Coordinating Center is responsible for distributing all IND Action Letters or Safety Reports to all participating institutions for submission to their individual IRBs for action as required.*
- *Mechanisms will be in place to ensure quality assurance, protocol compliance, and adverse event reporting at each site.*
- *Except in very unusual circumstances, each participating institution will order the study agent(s) directly from supplier. A participating site may order the agent(s) only after the initial IRB approval for the site has been forwarded to the Coordinating Center.*

13. REGULATORY CONSIDERATIONS

13.1 Protocol Review and Amendments

This protocol, the proposed informed consent and all forms of participant information related to the study (e.g., advertisements used to recruit participants) and any other necessary documents must be submitted, reviewed and approved by a properly constituted IRB governing each study location.

Any changes made to the protocol must be submitted as amendments and must be approved by the IRB prior to implementation. Any changes in study conduct must be reported to the IRB. The DF/HCC Overall Principal Investigator will disseminate protocol amendment information to all participating investigators.

All IRB decisions concerning the conduct of the study must be made in writing.

13.2 Informed Consent

All participants must be provided a consent form describing this study and providing sufficient information for participants to make an informed decision about their participation in this study. The formal consent of a participant, using the IRB approved consent form, must be obtained before the participant is involved in any study-related procedure. The consent form must be signed and dated by the participant or the participant's legally authorized representative, and by the person obtaining the consent. The participant must be given a copy of the signed and dated consent document. The original signed copy of the consent document must be retained in the medical record or research file.

13.3 Ethics and Good Clinical Practice (GCP)

CONFIDENTIAL

This document is confidential. Do not disclose or use except as authorized.

This study is to be conducted according to the following considerations, which represent good and sound research practice:

- E6 Good Clinical Practice: Consolidated Guidance
www.fda.gov/downloads/RegulatoryInformation/Guidances/UCM129515.pdf
- US Code of Federal Regulations (CFR) governing clinical study conduct and ethical principles that have their origin in the Declaration of Helsinki
 - Title 21 Part 11 – Electronic Records; Electronic Signatures
www.access.gpo.gov/nara/cfr/waisidx_02/21cfr11_02.html
 - Title 21 Part 50 – Protection of Human Subjects
www.access.gpo.gov/nara/cfr/waisidx_02/21cfr50_02.html
 - Title 21 Part 54 – Financial Disclosure by Clinical Investigators
www.access.gpo.gov/nara/cfr/waisidx_02/21cfr54_02.html
 - Title 21 Part 56 – Institutional Review Boards
www.access.gpo.gov/nara/cfr/waisidx_02/21cfr56_02.html
 - Title 21 Part 312 – Investigational New Drug Application
www.access.gpo.gov/nara/cfr/waisidx_02/21cfr312_02.html
- State laws
- DF/HCC research policies and procedures
<http://www.dfhcc.harvard.edu/clinical-research-support/clinical-research-unit-cru/policies-and-procedures/>

It is understood that deviations from the protocol should be avoided, except when necessary to eliminate an immediate hazard to a research participant. In such case, the deviation must be reported to the IRB according to the local reporting policy.

13.4 Study Documentation

The investigator must prepare and maintain adequate and accurate case histories designed to record all observations and other data pertinent to the study for each research participant. This information enables the study to be fully documented and the study data to be subsequently verified.

Original source documents supporting entries in the case report forms include but are not limited to hospital records, clinical charts, laboratory and pharmacy records, recorded data from automated instruments, microfiches, photographic negatives, microfilm or magnetic media, and/or x-rays.

13.5 Records Retention

All study-related documents must be retained for the maximum period required by applicable federal regulations and guidelines or institutional policies.

14. STATISTICAL CONSIDERATIONS

This sequential biomarker driven screening design is designed to identify promising treatments worthy of additional study.

Co Primary Endpoint

The primary endpoints for this trial is safety and tolerability defined as the number of DLTs and volumetric response as defined in section 10.1.

Secondary Endpoints:

Secondary endpoints include disease response according to RECIST 1.1, pathologic response, local failure rate, regional failure rate, local and regional progression free survival, disease-free survival, and overall survival. All are defined in Section 10.1.

Sample Size and Study Duration:

Because the use of nivolumab with or without ipilimumab is relatively novel in this setting, we will complete a safety run-in prior in each cohort prior to enrolling additional patients. If a single patient in either cohort is permanently unable to undergo surgery as a result of investigational treatment, enrollment to that cohort will close other DLTs are defined in Section 5.4. If this occurs in the nivolumab cohort then the study will close. The safety run in will begin and complete for nivolumab cohort before enrollment begins on the safety-run in ipilimumab cohort. Once both safety run-ins are complete, patients will be randomized to one of the two cohorts. If at any point during the study only one cohort is open for enrollment, all patients will be assigned to that cohort.

The safety run in for each cohort will follow a typical 3+3 design in each cohort. Initially 3 patients will be entered. If 0 out of 3 patients experiences dose-limiting toxicity (DLT), the safety run in will end and the study will proceed. If exactly 1 out of 3 patients has a DLT, an additional 3 patients will be entered in the safety run in. If none of the next 3 patients experiences a DLT, the study will proceed. If at any time 2 (or more) patients experience DLT, the study will terminate. Either arm will be considered promising if the safety run in is successfully completed.

Additionally, either arm (nivolumab or nivolumab combined with ipilimumab) will be considered promising and worthy of further evaluation if there is strong evidence that the response rate in either arm evaluated independently may be at least 15% (number of patients with volumetric response versus total number of patients treated in that arm). Response rates will also be correlated with RECIST and pathologic response and changes in lymphocyte infiltration of primary tumor deposits.

The decision rule will be based on the lower bound of the one-sided, 90% exact binomial confidence interval. With this criteria, the treatment will be considered promising if 6 or more of the 20 patients (including patients in the safety-run in) in either arm demonstrate a response. This

would correspond to a lower confidence bound that is at least 15%. If none of the first 10 patients in either arm have a response, then enrollment will stop. Analyses of response rates will be presented by treatment arm within disease accompanied by exact 80% confidence intervals. For a sample of size 20 per arm, each confidence interval will be no wider than 0.32. We will also estimate an aggregated response rate for each treatment modality and present with 80% exact confidence intervals.

Correlative studies will be largely exploratory in nature. We will attempt to correlate PD-L1 expression, mutational burden, T-cell infiltration and initial tumor burden with volumetric, RECIST and pathologic response. We will measure changes in radiologic and pathologic parameters and IHC staining over the course of therapy and correlate these with response and changes in immune markers present in the peripheral circulation.

The accrual goal for this study is 40 patients. We anticipate enrolling approximately 2 patients per month. Therefore, we expect to completely accrue to this study in approximately 20 months. The results should be made public within 24 months of reaching the end of the study. The end of the study is the time point at which the last data items are reported or after the outcome data are sufficiently mature for analysis, as defined above.

Analysis of Endpoints:

The primary endpoint is volumetric response, which will be assessed among all patients who initiate protocol therapy. Response will be assessed as defined in section 10.1. The response rate will be reported with 90% exact confidence intervals.

All patients who initiate protocol therapy will also be evaluated for response using RECIST v1.1, pathologic response at the time of surgery, safety and tolerability, local failure rate, regional failure rate, local and regional progression free-survival and overall survival. PFS and OS will be analyzed using Kaplan–Meier product-limit estimates and will be plotted using Kaplan-Meier plots. PFS is defined as the time from study randomization to disease progression according RECIST 1.1, medical judgment or death due to any cause, whichever occurred first. Patients alive without disease progression are censored at the date of last disease evaluation. The hazard ratio for each time-to-event endpoint will be estimated with 95% confidence intervals derived from the Cox proportional hazard model, but no hypothesis testing will be conducted. Other definitions are provided in section 10.1.

All patients will be evaluable for toxicity from the time of their first treatment with any study agent. Toxicity will be graded according to NCI CTCAE, Version 4.0. Toxicities will be summarized by maximum grade and by treatment arm. Incidence rate of each toxicity will be reported with 95% exact CI.

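### After a 3-to-6-patient run-in, no boundary on the overall DLT count covers the other 14 to 17 patients per arm, although DLT count is a co-primary endpoint

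*Combined protocol and SAP*

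**What the plan says.** Section 14 names two primary endpoints: "The primary endpoints for this trial is safety and tolerability defined as the number of DLTs and volumetric response as defined in section 10.1". Later in the same section, the analysis paragraph names only one: "The primary endpoint is volumetric response, which will be assessed among all patients who initiate protocol therapy".

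The DLT rule belongs to the run-in: "The safety run in for each cohort will follow a typical 3+3 design in each cohort". With no DLT in three patients, "If 0 out of 3 patients experiences dose-limiting toxicity (DLT), the safety run in will end and the study will proceed". With one in three, three more are entered: "If none of the next 3 patients experiences a DLT, the study will proceed". Then comes "If at any time 2 (or more) patients experience DLT, the study will terminate", with no statement of when that rule lapses. The paragraph closes by calling an arm promising once its run-in is completed.

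One further safety rule in Section 14 is not tied in its wording to the run-in. A single patient permanently unable to have surgery because of treatment closes that cohort, or the whole study if it happens in the nivolumab cohort. Section 5.4 counts inability to have the planned surgery as one type of DLT.

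Each arm has 20 patients, run-in included. The later numeric rules concern response only: enrolment stops if none of the first 10 respond, and "the treatment will be considered promising if 6 or more of the 20 patients" respond. Toxicities in all treated patients are summarised by arm with 95% exact intervals and no threshold. In Section 12.2, "The DSMC will meet quarterly and/or more often if required to review toxicity and accrual data". DLT information is among the items the committee may receive, and no count is given that would prompt action.

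**The concern.** The DLT count is a co-primary endpoint for every treated patient, but the plan acts on the overall count only in the first 3 or 6 patients of a cohort. Section 5.4 justifies the run-in by the relative novelty of preoperative use. Three to six patients do little to settle that question, and most of each arm is treated afterwards.

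Two things are at stake. Most DLT types in Section 5.4, such as grade 3 or higher toxicity outside the listed exceptions, could accumulate after the run-in without reaching any pre-stated count. At the end, the plan does not say how the co-primary DLT count is judged at 20 patients: the safety part of the promising label rests on the run-in, and the 6-of-20 criterion does not look at DLTs.

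**Working it through.** **Inputs.** From Section 14: the 3+3 rule, 20 patients per arm including the run-in, the one-sided 90% exact lower bound, the 6-of-20 cut-off, and accrual of about 2 patients a month. From Section 2.1.2.3: 6 of 28 patients (21%) with dose-limiting events. That is the only DLT rate the documents give as a percentage, and it comes from a melanoma phase 1 study on other schedules. The documents state no tolerable DLT rate, so every other rate below is an assumption.

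**The plan's own figure.** The one-sided 90% exact lower bound is the 10th percentile of Beta(x, n−x+1). It is 0.166 at 6/20 and 0.127 at 5/20, so 6 is the correct cut-off for 15%. The response rule reproduces.

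**Remaining patients.** 20 − 3 = 17 after a 0/3 exit; 20 − 6 = 14 after a 1/6 exit.

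**Passing the run-in.** With true DLT rate p and q = 1 − p:

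P(pass) = q³ + 3pq² × q³

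At p = 1/6 this is 0.579 + 0.201 = 0.780. At p = 1/3 it is 0.296 + 0.132 = 0.428.

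**Further DLTs after a pass.** Expected number = p × [17 × share leaving at 3 + 14 × share leaving at 6]. At p = 1/3 the share leaving at 3 is 0.296/0.428 = 0.692. The mean number of further patients is 17 × 0.692 + 14 × 0.308 = 16.08, and 16.08/3 = 5.4.

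| True DLT rate | P(pass run-in) | Expected further DLTs |
|---|---|---|
| 10% | 91% | 1.6 |
| 1/6 | 78% | 2.7 |
| 6/28 | 68% | 3.5 |
| 25% | 60% | 4.0 |
| 1/3 | 43% | 5.4 |

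**What the run-in shows.** The upper limit of the two-sided 95% exact interval for the DLT rate is 71% after 0/3 and 64% after 1/6.

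**Scope of the two-DLT sentence.** If it covered all 20 patients of an arm, the chance of crossing it would be 1 − q²⁰ − 20pq¹⁹. That is 26% at a 5% DLT rate, 1 − 0.122 − 0.270 = 61% at 10%, and 93% at 20%. If it covers the run-in only, nothing replaces it afterwards.

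**An illustrative review boundary.** Take Section 14's one-sided 90% exact lower bound and, as an example reference, 1/6, the highest proportion the run-in accepts. Pause when the bound exceeds 1/6:

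- 3 DLTs by patient 7 (bound 0.170)
- 4 by patient 11 (0.169)
- 5 by patient 15 (0.172)
- 6 by patient 19 (0.175)

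The exact chance of a pause was computed patient by patient, starting from the two ways of passing the run-in (0/3 and 1/6):

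| True DLT rate | P(pause, given run-in passed) |
|---|---|
| 10% | 1% |
| 1/6 | 7% |
| 20% | 13% |
| 6/28 | 16% |
| 25% | 26% |
| 1/3 | 51.5% |
| 40% | 71% |

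**The case against.** The strongest reply is that the plan already has later safeguards, and much of it stands.

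A reader might infer that nothing at all limits DLTs after the run-in. The documents do not support that. The loss-of-surgery rule acts on a single patient, is not confined to the run-in, and concerns an event that Section 5.4 defines as a DLT. What is absent is a boundary on the overall count, since the surgery rule covers one DLT type among many.

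A reader might also infer that safety plays no part in calling an arm promising. It does: completing the run-in is itself a criterion, and response is introduced as an additional one. But that safety criterion rests on 3 to 6 patients.

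The two-DLT sentence could be read as covering the whole trial, in which case a boundary exists and the illustration above would loosen it. The sentence sits in the run-in paragraph, between the six-patient exit and the run-in verdict, so the run-in reading is the natural one. A rule crossed 61% of the time at a 10% DLT rate would fit poorly with a plan for 20 patients per arm. Still, its scope is unstated.

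DSMC review is real oversight and can be called more often than quarterly. At 2 patients a month, about 2 × 3 = 6 patients enrol between quarterly meetings, and no count tells the team when an earlier meeting is needed.

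Finally, the documents expect a single 1 mg/kg ipilimumab dose to be less toxic than earlier schedules, and a later boundary gains most at high DLT rates. That is fair. Near the quoted 21%, the illustrative boundary pauses only 16% of the cohorts that passed. The choice of reference rate is a clinical judgement for the sponsor and the DSMC.

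**Conclusion.** The point holds in this form: after the run-in, no boundary on the overall DLT count applies to the remaining 14 to 17 patients per arm, the scope of the two-DLT sentence is unstated, and the 6-of-20 criterion has no DLT component. Section 14 also does not say how the co-primary DLT count is judged at 20 patients, and its two statements of the primary endpoint disagree.

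The size depends on the true DLT rate. At 10% the gap matters little (1.6 further DLTs expected). At one third, 43% of cohorts pass and about 5.4 further DLTs follow. These figures assume independent patients with a constant DLT rate, full accrual to 20, and the run-in reading of the two-DLT sentence. They set aside the surgery rule and any DSMC action, either of which could stop a cohort sooner. This is an inexpensive improvement to the design and does not put the response rule in doubt.

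**What to change.** In Section 14:

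1. State the scope of both existing rules: that the two-DLT rule applies to the run-in only, if that is what is meant, and that the surgery rule applies throughout. If the two-DLT rule is meant to run longer, reconcile it with the 20-patient plan, given the crossing probabilities above. This comes first, because item 2 depends on it.
2. Carry the DLT count through all 20 patients of each cohort, with a pre-stated count that pauses enrolment to that cohort for DSMC review. The sponsor and DSMC set the reference rate. The 3-by-7, 4-by-11, 5-by-15, 6-by-19 schedule is an illustration at 1/6.
3. Report the DLT rate per arm over all treated patients, with an exact interval, beside the response verdict. Make the analysis paragraph agree with the co-primary statement.

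The cost is a short paragraph and no new data: DLTs are already recorded, and the Section 5.4 window closes at surgery. The downside is a small chance of an unneeded pause, about 1% at a 10% DLT rate and 7% at 1/6 under the illustration.
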